6.14.3.14.1. Acute Renal Events

Because severe GI events may lead to dehydration, which could cause a deterioration in renal function including acute renal failure, dehydration events will be analyzed. Acute renal events associated with chronic renal failure exacerbation will also be captured.

Severe/serious renal events from the following SMQ search will be considered AESIs.

The counts and percentages of participants with acute renal events will be summarized by treatment by using the MedDRA PTs contained in any of the following SMQs:

- Acute renal failure: Narrow terms in Acute renal failure SMQ (20000003) and
- Chronic kidney disease: Narrow terms in Chronic kidney disease SMQ (20000213).

In addition, a listing of participants with treatment-emergent acute renal events may be provided, if deemed necessary.

6.14.3.14.2. Dehydration

Dehydration events will be captured in the Narrow terms in Dehydration SMQ (20000232). Severe/serious dehydration events will be considered AESIs.

A listing of participants with treatment-emergent dehydration events will be provided.

6.14.3.15. Thyroid Safety Monitoring

6.14.3.15.1. Calcitonin

Observed calcitonin data (a thyroid-specific laboratory assessment) will be summarized by treatment and nominal visit.

The counts and percentages of participants with a maximum postbaseline calcitonin value in the following thresholds will be provided by treatment and baseline calcitonin value (≤ 20 ng/L, >20 ng/L to ≤ 35 ng/L, >35 ng/L). Postbaseline: ≤ 20 ng/L, >20 ng/L to ≤ 35 ng/L, >35 ng/L to ≤ 50 ng/L, >50 ng/L to ≤ 100 ng/L, and >100 ng/L.

6.14.3.15.2. C-Cell Hyperplasia and Thyroid Malignancies

Treatment-emergent thyroid malignancies and C-Cell hyperplasia will be considered AESIs. Detailed searching criteria can be found in [Appendix 3](#).

The counts and percentages of participants with treatment-emergent thyroid C-cell hyperplasia and malignancies will be summarized by treatment and PT ordered with decreasing frequency. In addition, a listing of participants with treatment-emergent thyroid C-cell hyperplasia and neoplasms may be provided if deemed necessary.

6.14.3.16. Treatment-Emergent Supraventricular Arrhythmias and Cardiac Conduction Disorders

Severe/serious treatment-emergent supraventricular arrhythmias and cardiac conduction disorders will be considered AESIs.

The treatment-emergent supraventricular arrhythmias and cardiac conduction disorders events will be identified using the MedDRA PTs. Detailed searching criteria can be found in [Appendix 3](#).

The counts and percentages of participants with treatment emergent supraventricular arrhythmias and cardiac conduction disorders will be summarized by treatment and PT nested within SMQ. The PT will be ordered with decreasing frequency within SMQ. A listing of participants with treatment-emergent supraventricular arrhythmias and cardiac conduction disorders may be provided if deemed necessary.

6.14.3.17. Overdose

A listing of participants reporting AEs related to overdosing of tirzepatide will be provided.

6.14.3.18. Abuse Liability

The counts and percentages of participants with treatment emergent potential abuse liability events will be summarized by treatment group with decreasing frequency. Detailed searching criteria can be found in [Appendix 3](#).

6.14.4. Vital Signs

In the case that multiple records of an individual vital sign are collected at the same visit, they will be averaged prior to being used for data summaries and analyses.

Descriptive summaries by treatment and by nominal visit will be provided for baseline and postbaseline values as well as change from baseline values.

An MMRM and/or an ANCOVA model as in Section [6.14](#) might be conducted if necessary.

Counts and percentages of participants with treatment-emergent abnormal sitting SBP, sitting DBP, and pulse at any time during the entire study (including the off-drug follow up time period) will be presented by treatment for participants who have both baseline and at least 1 postbaseline result. A treatment-emergent high result is defined as a change from a value less than or equal to the high limit at baseline to a value greater than the high limit at any time that meets the specified change criteria during the postbaseline period. A treatment-emergent low result is defined as a change from a value greater than or equal to the low limit at baseline to a value less than the low limit at any time that meets the specified change criteria during the postbaseline period. To assess decreases, change from the minimum value during the baseline period to the minimum value during the postbaseline period will be used. To assess increases, changes from the maximum value during the baseline period to the maximum value during the postbaseline period will be used. Both planned and unplanned measurements will be included in the analysis. The criteria for identifying participants with treatment-emergent vital sign abnormalities are stated in [Table GPHK.6.11](#).

Table GPHK.6.11. Categorical Criteria for Abnormal Treatment-Emergent Blood Pressure and Pulse Measurements

Parameter	Low	High
Systolic BP (mm Hg) (Supine or sitting – forearm at heart level)	≤90 and decrease from baseline ≥20	≥140 and increase from baseline ≥20
Diastolic BP (mm Hg) (Supine or sitting – forearm at heart level)	≤50 and decrease from baseline ≥10	≥90 and increase from baseline ≥10
Pulse (bpm) (Supine or sitting)	<50 and decrease from baseline ≥15	>100 and increase from baseline ≥15

Abbreviations: BP = blood pressure; bpm = beats per minute

In addition, following analyses will be conducted by treatment:

- counts and percentages of participants who had resting heart rate changes from baseline at 2 consecutive visits of more than 10 bpm and/or 20 bpm
- counts and percentages of participants who had resting heart rate maximum changes from baseline at visit <20 bpm or ≥20 bpm
- counts and percentages of participants who had at least 1 resting heart rate exceeding 100 bpm, and
- counts and percentages of participants who had at least 1 resting heart rate exceeding 100 bpm occurring at 2 consecutive study visits.

6.14.5. Electrocardiograms

For electrocardiogram (ECG) parameters that collect in triplicates (that is, Visit 3 and Visit 12), the average from the 3 measurements for the same parameter at the same visit will be calculated and used for all the subsequent summaries and analyses.

Summary statistics by treatment and by nominal visit will be provided for ECG parameters (heart rate, PR, QRS, QT, and QT corrected using Fredericia's correction factor [$QTcF = QT / RR^{0.333}$]). When the QRS is prolonged (for example, a complete bundle branch block), QT and QTc should be used to assess ventricular repolarization. Thus, for a particular ECG, the following will be set to missing (for analysis purposes) when QRS is ≥120 msec: QT and QTcF.

Change from baseline to postbaseline values for ECG parameters (heart rate [HR] and PR) will be summarized for participants who have both a baseline and at least 1 postbaseline result. Only planned measurements will be included in the mean change analyses.

The criteria for identifying participants with treatment-emergent quantitative ECG abnormalities is based on [Table GPHK.6.12](#).

The counts and percentages of participants who meet following criteria at any time during the entire study period (including the off-drug follow up time period) will be summarized by treatment group:

- treatment-emergent ECG abnormalities as listed in [Table GPHK.6.12](#)
- QT greater than 500 msec
- QTcF greater than 500 msec, and
- treatment-emergent increase from the maximum baseline in QTcF interval of greater than 30 msec, 60 msec, or 75 msec. Maximum baseline will be the maximum non-missing observation in the baseline period. The maximum value during the treatment period will be analyzed. Scheduled and unscheduled measurements will be included.

Table GPHK.6.12. Selected Categorical Limits for ECG Data

Parameter	Low		High	
	Males	Females	Males	Females
Heart Rate (bpm)	<50 and decrease ≥ 15	<50 and decrease ≥ 15	>100 and increase ≥ 15	>100 and increase ≥ 15
PR Interval (msec)	<120	<120	≥ 220	≥ 220
QRS Interval (msec)	<60	<60	≥ 120	≥ 120
QTcF (msec)	<330	<340	>450	>470

Abbreviations: bpm = beats per minute; ECG = electrocardiogram; QTcF = Fredericia's corrected QT interval.

6.14.6. Clinical Laboratory Evaluation

Limits from the performing lab will be used to define low (L) and high (H). Descriptive summaries by treatment and by nominal visit will be provided for the baseline and postbaseline values as well as the change from baseline values. The associated descriptive will be presented in System International (SI) units and in conventional (CN) units.

Observed and change from baseline values for each visit may be displayed in plots for participants who have both a baseline and at least 1 postbaseline planned measurement. Baseline will be the last non missing observation prior to taking first study drug. Unplanned measurements will be excluded from plots.

A shift table will be provided including unplanned measurements. The shift table will include the number and percentage of participants within each baseline category (low, normal, high, or missing) versus each postbaseline category (low, normal, high, or missing) by treatment. The proportion of participants shifted will be compared between treatments using Fisher's exact test.

For qualitative laboratory analytes, the number and percentage of participants with normal and abnormal values will be summarized by treatment.

A listing of abnormal findings will be created for laboratory analyte measurements, including qualitative measures. The listing will include participant identification, treatment group, laboratory collection date, study day, analyte name, and analyte finding.

The MMRM model or ANCOVA (if MMRM model is not applicable) will be used for the analysis during the treatment period for the continuous measurements for selected lab tests.

6.14.6.1. Two-hour Oral Glucose Tolerance Test (OGTT)

The following parameters will be collected during 2-hour OGTT for each scheduled OGTT visit:

- glucose
- insulin, and
- C-peptide.

For each above parameter, the mean concentration over 120 minutes plots will be created by glycemia status at randomization and by treatment group and by OGTT visit (that is, at baseline and at Week 72). After 72 week, these plots will be created for participants with prediabetes at randomization.

For each above parameter, the area under the curve from time zero to 2 hours ($AUC_{(0-2h)}$) during OGTT will be calculated using the trapezoidal rule. The respective $AUC_{(0-2h)}$ will be summarized by treatment group and by OGTT visit.

In addition, the following OGTT derived parameters (Armato et al. 2018) will be calculated at each OGTT visit for each participants with OGTT:

- Glycemic response categories:
 - Normal: normal glucose tolerance and a 1-hour PG concentration <8.6 mmol/L (154.8 mg/dL), where normal glucose tolerance is defined by the 2019 American Diabetes Association Standards of Medical Care in Diabetes (ADA 2019a) as follows:
 - Fasting glucose: obtained alone or at time = 0 during an OGTT is <100 mg/dL (5.6 mmol/L) **and**
 - 2-hour glucose: obtained at time = 120 minutes during an OGTT is <140 mg/dL (7.8 mmol/L)
 - Moderate impairment:
 - Normal glucose tolerance and 1-hour plasma glucose ≥ 8.6 mmol/L, **or**
 - Impaired fasting glucose or impaired glucose tolerance, or both, and 1-hour PG concentration <8.6 mmol/L (154.8 mg/dL), where impaired fasting glucose is defined as fasting plasma glucose (FPG) levels between 100 and 125 mg/dL (between 5.6 and 6.9 mmol/L), and impaired glucose tolerance is defined as 2-hour PG during 75 g OGTT levels between 140 and 199 mg/dL (between 7.8 and 11.0 mmol/L) (ADA 2019a)
 - Severe abnormality: impaired fasting glucose or impaired glucose tolerance, or both, and 1-hour PG concentration ≥ 8.6 mmol/L

- Matsuda Index = $\frac{10000}{\sqrt{(FPG \times FPI) \times (\bar{G} \times \bar{I})}}$, where FPG is the fasting glucose, FPI is the fasting insulin, \bar{G} denotes the mean glucose during OGTT, and \bar{I} denotes the mean insulin during OGTT
 - Normal insulin sensitivity: Matsuda index >25th percentile of Matsuda index values from participants with normal glucose tolerance at baseline
 - Moderate insulin resistance: Matsuda index in the 5th to 25th percentile (inclusive) of Matsuda index values from participants with normal glucose tolerance at baseline
 - Severe insulin resistance: Matsuda index < the lowest fifth percentile of the range of Matsuda index values from participants with normal glucose tolerance at baseline
- Insulin secretion = $\left(\frac{\Delta C_{\text{pep}}}{\Delta G}\right)_{0-120}$, where ΔC_{pep} denotes the incremental area under the plasma C-peptide curve during the 2-hour OGTT, and ΔG denotes the incremental area under the plasma glucose concentration curve during 2-hour OGTT
 - Insulin secretion index = $\frac{\left(\frac{\Delta C_{\text{pep}}}{\Delta G}\right)_{0-120}}{\text{normal level of insulin secretion}}$, where normal level of insulin secretion is the median value for insulin secretion, ie, $\left(\frac{\Delta C_{\text{pep}}}{\Delta G}\right)_{0-120}$, in participants with normal glucose tolerance at baseline
 - Normal insulin secretion: insulin secretion index >70%
 - Moderate impairment of insulin secretion: 50% to 70% (inclusive) of the insulin secretion index
 - Severe impairment of insulin secretion: <50% of the insulin secretion index
- β -cell function = Insulin secretion * Matsuda index = $\left(\frac{\Delta C_{\text{pep}}}{\Delta G}\right)_{0-120} * \frac{10000}{\sqrt{(FPG \times FPI) \times (\bar{G} \times \bar{I})}}$

The descriptive summaries for the above continuous derived OGTT parameters (for example, sample size, mean, median, SD, minimum, maximum) will be calculated at each scheduled OGTT visit by treatment group and by glycemia status (that is, normoglycemia and prediabetes at randomization) if applicable. For the categorical derived OGTT parameters, descriptive summaries (that is, sample size, frequency, percentage) will be calculated at each scheduled OGTT visit by treatment group and by glycemia status (that is, normoglycemia and prediabetes at randomization) if applicable.

Unless other specified, the ANOVA model will be applied to the following parameters with terms of treatment groups (tirzepatide 5 mg, 10 mg, 15 mg, and placebo) and baseline value of the corresponding parameter at 72 weeks. For the measurements assessed at 176 weeks, MMRM model might apply for participants with prediabetes at baseline.

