4.1.2.1. Definition of Prediabetes

The duration of treatment in Study GPHK (SURMOUNT-1) is determined by glycemic status at randomization, categorized into those with prediabetes or normoglycemia (participants with T2DM are excluded), as defined by the 2019 American Diabetes Association Standards of Medical Care in Diabetes (American Diabetes Association 2019b). The following populations are defined:

	Normoglycemia	Prediabetes	Diabetes
Fasting glucose Obtained alone or at time = 0 during an OGTT	<100 mg/dL (<5.6 mmol/L)	100-125 mg/dL (5.6-6.9 mmol/L)	≥126 mg/dL (≥7.0 mmol/L)
2H glucose Obtained at time = 120 min during an OGTT	<140 mg/dL (<7.8 mmol/L)	140-mg-199 mg/dL (7.8-11.0 mmol/L)	≥200 mg/dL (≥11.1 mmol/L)
HbA1c	<5.7% (<39 mmol/mol)	5.7%-6.4% (39-47 mmol/mol)	≥6.5% (≥48 mmol/mol)

Abbreviations: H = hour; HbA1c = hemoglobin A1c; OGTT = 2-hour oral glucose tolerance test.

Screening to determine randomization glycemic status will occur in 2 visits:

Screening Visit 1

Participants will have a fasting glucose (FG) and HbA1c test. Results of these tests determine eligibility to proceed to Screening Visit 2.

- FG ≥126 mg/dL (7.0 mmol/L) OR HbA1c ≥6.5% (48 mmol/mol) suggests DM. These participants are **excluded** from the study and should be referred to their primary care physician for further work-up to confirm the diagnosis.

- All participants otherwise eligible and without FG or HbA1c values suggestive of diabetes will proceed to Screening Visit 2

Screening Visit 2

All participants attending Screening Visit 2 will undergo a 2-hour OGTT test. These results, in combination with those obtained from Screening Visit 1, will be used to determine study eligibility and randomization glycemic status.

- 2-hour OGTT results: FG ≥ 126 mg/dL (≥ 7.0 mmol/L) OR 2-hour OGTT ≥ 200 mg/dL (≥ 11.1 mmol/L) suggests diabetes mellitus. These participants are ***excluded*** from the study and should be referred to their primary care physician for further work-up to confirm the diagnosis.

Glycemic Classification

All participants without laboratory tests suggestive of diabetes will be classified as having either normoglycemia or prediabetes. In keeping with American Diabetes Association guidelines (American Diabetes Association 2019b), at least 2 abnormal tests are required to diagnose prediabetes. For example:

- Both 0 AND 2-hour values during the 2-hour OGTT values are in the prediabetes range.
- FG at Screening Visit 1 AND Visit 2 are in the prediabetes range.

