5.2. Exclusion Criteria

Participants are excluded from the study if any of the following criteria apply:

Medical Conditions***Diabetes-related***

6. Have type 1 diabetes mellitus (T1DM) or T2DM, history of ketoacidosis, or hyperosmolar state/coma
7. Have laboratory evidence diagnostic of diabetes mellitus during screening, including 1 or more of: HbA1c $\geq 6.5\%$ (≥ 48 mmol/mol), FG ≥ 126 mg/dL (≥ 7.0 mmol/L), random glucose or 2-hour glucose measurement from a 2-hour OGTT ≥ 200 mg/dL (≥ 11.1 mmol/L)

Obesity-related

8. Have a self-reported change in body weight >5 kg within 3 months prior to screening
9. Have a prior or planned surgical treatment for obesity (excluding liposuction or abdominoplasty if performed >1 year prior to screening)
10. Have or plan to have endoscopic and/or device-based therapy for obesity or have had device removal within the last 6 months (for example, mucosal ablation, gastric artery embolization, intragastric balloon and duodenal-jejunal bypass sleeve)

Other medical

11. Have renal impairment measured as estimated glomerular filtration rate (eGFR) <30 mL/min/1.73 m², calculated by Chronic Kidney Disease-Epidemiology as determined by central laboratory during screening
12. Have a known clinically significant gastric emptying abnormality (for example, severe diabetic gastroparesis or gastric outlet obstruction) or chronically take drugs that directly affect GI motility
13. Have had a history of chronic or acute pancreatitis
14. Have thyroid-stimulating hormone (TSH) outside of the range of 0.4 to 6.0 mIU/L at screening visit

Note: Patients receiving treatment for hypothyroidism may be included, provided their thyroid hormone replacement dose has been stable for at least 3 months.

Note: TSH values above the normal range can, in some patients, suggest subclinical hypothyroidism. If, in the investigator's opinion, the participant has subclinical hypothyroidism and may require initiation of thyroid hormone replacement during the course of the study, the patient should be excluded from the study.

15. Have obesity induced by other endocrinologic disorders (for example, Cushing Syndrome) or diagnosed monogenetic or syndromic forms of obesity (for example, Melanocortin 4 Receptor deficiency or Prader Willi Syndrome)

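### The OGTT glycemic response categories in SAP 6.14.6.1 have no diabetes-range level, so some of the worst post-baseline results are unclassified while mixed ones are labelled Moderate or Severe

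*SAP*

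**What the plan says.** SAP 6.14.6.1 defines three glycemic response categories, citing a published source.

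- "Normal: normal glucose tolerance and a 1-hour PG concentration" below 8.6 mmol/L (154.8 mg/dL), where normal tolerance means FPG <100 and 2-hour glucose <140 mg/dL.
- Moderate impairment: normal tolerance with a 1-hour value of 8.6 mmol/L or more, or impaired fasting glucose and/or impaired glucose tolerance with a 1-hour value below 8.6 mmol/L.
- "Severe abnormality: impaired fasting glucose or impaired glucose tolerance, or both, and 1-hour PG concentration" of 8.6 mmol/L or more.

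Both impaired ranges are closed at the top: "impaired fasting glucose is defined as fasting plasma glucose (FPG) levels between 100 and 125 mg/dL" and "impaired glucose tolerance is defined as 2-hour PG during 75 g OGTT levels between 140 and 199 mg/dL". The derived parameters "will be calculated at each OGTT visit for each participants with OGTT". For reporting: "For the categorical derived OGTT parameters, descriptive summaries (that is, sample size, frequency, percentage) will be calculated at each scheduled OGTT visit". The section gives no diabetes level, no other or unclassified row, and no rule on whether an unclassifiable result counts in the denominator.

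Elsewhere the plan does recognise the diabetes range. The glycemic status table in Protocol 4.1.2.1 has a diabetes column, with fasting glucose "≥126 mg/dL (≥7.0 mmol/L") and 2-hour glucose ≥200 mg/dL. SAP Table GPHK.6.3 repeats it, and the exploratory shift analysis in SAP Table GPHK.6.6 includes a T2DM level.

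**The concern.** Categories meant for every participant at every OGTT visit should cover every possible result and should not improve, or disappear, as glucose gets worse. Here the caps mean that a value can rise out of the impaired range and take the participant out of the classification.

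The clearest case is a result with both values in the diabetes range. Under Protocol 4.1.2.3, two such values at one visit establish incident diabetes. Under Protocol 4.1.2.2, the OGTT is then omitted at later visits. That participant is unclassified at the diagnosing visit and untested afterwards, so the progression never shows in this table.

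At stake are the reported percentages in a descriptive table by treatment group. A reader would take Severe to be the worst end of the scale, and it is not.

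**Working it through.** The documents give no figure to reproduce here, so the check is an enumeration.

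**Inputs.** FPG bands <100, 100–125 and ≥126 mg/dL; 2-hour bands <140, 140–199 and ≥200 mg/dL; 1-hour bands <154.8 and ≥154.8 mg/dL (8.6 mmol/L). The category cut points come from SAP 6.14.6.1 and the diabetes cut points from Protocol 4.1.2.1. Values are taken as whole mg/dL.

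**Rule as written.** Each entry gives the category for 1-hour <8.6, then for 1-hour ≥8.6 mmol/L.

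| FPG | 2-hour <140 | 2-hour 140–199 | 2-hour ≥200 |
|---|---|---|---|
| <100 | Normal / Moderate | Moderate / Severe | none / none |
| 100–125 | Moderate / Severe | Moderate / Severe | Moderate / Severe |
| ≥126 | none / none | Moderate / Severe | none / none |

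**Counts.** There are 3 × 3 × 2 = 18 cells. Diabetes-range cells (FPG ≥126 or 2-hour ≥200) number 5 × 2 = 10. Of these, 3 × 2 = 6 have no category and 2 × 2 = 4 are labelled Moderate or Severe. All 8 remaining cells fall in exactly one category, and an integer grid of non-diabetic values shows no gaps or overlaps. The gap is therefore specific to the diabetes range.

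**Order.** Hold the 1-hour value at or above 8.6 mmol/L. FPG 120 with 2-hour 210 mg/dL is Severe, because fasting glucose is impaired. FPG 130 with 2-hour 210 mg/dL is in no category. A worse fasting value removes the participant from Severe.

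**When it can occur.** Not at baseline, as expected, because Protocol 5.2 excludes people who "Have laboratory evidence diagnostic of diabetes mellitus during screening". After baseline, the schedules in Protocol 1.3.1 and 1.3.2 place the OGTT at Weeks 72, 124 and 176 and at Visit 802, plus the early-discontinuation visit and Visit 199.

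**Direction within an arm.** Let N be the OGTTs at a visit, s the number Severe, and u the unclassified results with a 1-hour value ≥8.6 mmol/L. Counting these with Severe gives (s + u)/N. Leaving them unclassified gives s/N if they are kept in the denominator, or s/(N − u) if they are dropped. Since (s + u)(N − u) = sN + u(N − s − u) ≥ sN, both are no larger than (s + u)/N. If they are dropped, the Normal share also rises.

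**Scale.** Protocol 9.2 assumes 60% prediabetes and 3-year progression of 6% on placebo and 1.6% on tirzepatide.

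- Placebo: 0.60 × 600 = 360, and 360 × 0.06 = 21.6.
- Tirzepatide, all doses: 0.60 × 1800 = 1080, and 1080 × 0.016 = 17.3.
- Together about 39 expected progressors among 1440, before dropout.

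These are progressors by any route, not unclassified OGTTs.

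**The case against.** The strongest reply is that little depends on this table. It is a descriptive summary in the laboratory section, with no alpha. Participants with diabetes-range results are still captured by the glucose AUC summaries and mean curves in the same section, by the T2DM level in the exploratory shift analysis, by adjudication of reported or suspected cases (Protocol 4.1.2.3), and by the key secondary time to onset of T2DM (SAP Table GPHK.6.4). All of that stands.

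Three stronger readings are tempting, and the documents do not support them.

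- A reader might infer that every diabetes-range result is unclassified. It is not: one value in the impaired range is enough, so 4 of the 10 diabetes-range cells are labelled Moderate or Severe.
- A reader might take about 22 placebo and 17 tirzepatide progressors as the number lost from the table. Diabetes can also be established by HbA1c, fasting glucose between OGTT visits, symptomatic hyperglycemia or starting medication. Other progressors will fall in the classified mixed cells, and the plan assumes 49% dropout. In the other direction, an isolated, unconfirmed 2-hour value ≥200 mg/dL with normal fasting glucose is unclassified without being a progressor. Normoglycemic participants also have a Week 72 OGTT, for which no progression rate is given.
- A reader might conclude that a treatment comparison is biased by a known amount. The SAP does not say how unclassified results enter the denominator, and the counts by arm and visit cannot be derived.

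It may also be said that the caps come from the published scheme the SAP cites. That cannot be checked from the documents, and it would not make the scale exhaustive.

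**Conclusion.** The point holds as a minor defect in a stated rule, not merely missing detail. Read literally, the three categories leave 6 of 18 combinations empty, all in the diabetes range and including the pattern with both values diabetic, while 4 other diabetes-range combinations are placed in Moderate or Severe.

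The effect is limited to the post-baseline rows of one descriptive summary. No conclusion about diabetes progression rests on it. The number of results affected is not derivable: the roughly 39 expected progressors, plus isolated abnormal OGTTs, bound it only loosely. It is likely to be proportionally higher on placebo, if progression follows the 6% and 1.6% planning assumptions and unclassified OGTTs arise broadly in line with progression.

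**What to change.** Add a fourth level to SAP 6.14.6.1, diabetes range, defined as FPG ≥126 mg/dL or 2-hour glucose ≥200 mg/dL at that OGTT. State that it takes precedence over Moderate and Severe, and that these results stay in the denominator at each visit. The label should describe the test result, not a confirmed diagnosis, since Protocol 4.1.2.3 requires confirmation of a single abnormal value.

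With precedence, all 18 combinations fall in exactly one level: 1 Normal, 4 Moderate, 3 Severe and 10 diabetes range. Without precedence, the four mixed cells would belong to two levels. Removing the cap from Severe alone would not be enough, because the empty cells with a 1-hour value below 8.6 mmol/L would stay empty.

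The cost is one SAP definition and its programming, with no new data and no effect on alpha or the primary analysis. The small downside is that the table departs from a three-level scheme, which may limit comparison with the cited source, and that mixed results move out of Moderate and Severe.
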